2.4. Statistical Analyses

The study will estimate the difference between GSK3858279 and placebo on the endpoints described: UVB heat pain detection test, cold pressor time to intolerable pain threshold test and electrical pain tolerance threshold test in the PainCart scale.

All participants will receive GSK3858279 and placebo during their course on the study, depending on their randomisation schedule.

The primary endpoints are:

- Ratio to Baseline in UVB heat pain detection (Celsius)
- Ratio to Baseline in cold pressor time to intolerable pain threshold (seconds)
- Ratio to Baseline in electrical pain tolerance – single stimulus (mA)

If ratio to baseline is not suitable due to the distribution of the parameters, change from baseline will be utilised instead.

3. PLANNED ANALYSES

3.1. Interim Analyses

Two interim analyses of the primary endpoints to inform internal decision making may be conducted during the study. The interim analyses may occur when:

- The final UVB-MITT participant (approx. 15 evaluable participants) to have completed the day 15 assessments of the PainCart assessments in study period 3 (final study period).
- The final randomised participant has completed the day 15 assessments of the PainCart assessments in study period 3 (final study period).

The table below details the endpoints that will be analysed/summarised at the interim:

Purpose of Interim	Endpoints
Interim Analysis 1 (Futility)	
UVB heat pain detection (Celsius)
 
 • Absolute values (Summarised) • Change from baseline (Summarised) • Ratio to Baseline (Summarised) • AAUC of Ratio to Baseline (Analysed) 
Cold pressor time to intolerable pain threshold (seconds):
 
 • Absolute values (Summarised) • Change from baseline (Summarised) • Ratio to Baseline (Summarised) • AAUC of Ratio to Baseline (Analysed) 
Electrical pain tolerance – single stimulus (mA):
 
 • Absolute values (Summarised) • Change from baseline (Summarised) • Ratio to Baseline (Summarised) • AAUC of Ratio to Baseline (Analysed) 
Summary of Demographic Characteristics
 
Summary of Derived Serum GSK3858279 Pharmacokinetic Parameters (non-transformed and log-transformed)
 
Summary of Serum GSK3858279 Concentration-Time Data (ng/mL)
 
Summary of Derived Free and Total CCL17 in Serum Target Engagement Parameters (non-transformed and log-transformed)

	
Summary of Free & Total CCL17 in Serum Concentration-Time Data (pg/mL).
 
Summary of All Adverse Events by System Organ Class and Preferred Term by Period (>=2 Subjects with the AE)

IA 2 – Internal Decision-Making Purposes	
UVB heat pain detection (Celsius)
 
 • Absolute values (Summarised) • Change from baseline (Summarised) • Ratio to Baseline (Summarised) • AAUC of Ratio to Baseline (Analysed) 
Cold pressor time to intolerable pain threshold (seconds):
 
 • Absolute values (Summarised) • Change from baseline (Summarised) • Ratio to Baseline (Summarised) • AAUC of Ratio to Baseline (Analysed) 
Electrical pain tolerance – single stimulus (mA):
 
 • Absolute values (Summarised) • Change from baseline (Summarised) • Ratio to Baseline (Summarised) • AAUC of Ratio to Baseline (Analysed) 
Summary of Demographic Characteristics
 
Summary of All Adverse Events by System Organ Class and Preferred Term by Period

Note: Ratio to baseline will only be produced if deemed suitable by the distribution of the parameters.

Note: AAUC = Analysis Area Under Curve. Derivation of AAUC is described in Section [12.6.3](#) Pharmacodynamic.

The statistical methods of the analyses are described in Section [7.1](#), Section [7.2](#) and Section [7.3](#).

The following functions will be unblinded to interim analysis data: Clinical Statistics, Clinical Programming and CPMS. Other members of GSK will be unblinded to group level summary data following the interim analyses (as documented in the Interim Charter).

3.2. Final Analyses

The final planned primary analyses will be performed after the completion of the following sequential steps:

1. All participants have completed the study as defined in the protocol.

2. All required database cleaning activities have been completed and final database release (DBR) and database freeze (DBF) has been declared by Data Management.
3. All criteria for unblinding the randomization codes have been met.
4. Randomization codes have been distributed according to RandAll NG and RAMOS procedures.

4. ANALYSIS POPULATIONS

Population	Definition / Criteria	Analyses Evaluated
Screened	
 • All participants who were screened for eligibility 	
 • Study Population • Safety
Enrolled	
 • All participants who passed screening and entered the study. • Note screening failures (who never passed screening even if rescreened) and participants screened but never enrolled into the study (Reserve, Not Used) are excluded from the Enrolled population as they did not enter the study. 	
 • Study Population
Randomized	
 • All participants who were randomly assigned to treatment in the study. • This population will be based on the treatment sequence the participant was randomized to. 	
 • Study Population
Safety	
 • All randomized participants who received at least one dose of study treatment. • This population will be based on the treatment sequence the subject actually received. • Note: Participants who were not randomized but received at least one dose of study treatment should be included. 	
 • Safety • PK/PD
Pharmacokinetic (PK)	
 • All participants in the Safety population who had at least 1 non-missing serum PK assessment. • Note: Non-quantifiable [NQ] values will be considered as non-missing values 	
 • PK
Intent-To-Treat (ITT)	
 • All randomized participants who received at least one dose of study treatment. • This population will be based on the treatment sequence the subject was randomized to. • Any participants who receives a treatment randomization number will be considered to have been randomized. 	
 • PainCart • Study Population
Modified Intent-to-Treat (MITT)	
 • All randomized participants who received at least one dose of study treatment and completed at least one PainCart assessment in at least two study periods. • This population will be based on the treatment sequence the subject was randomized to. • Any participants who receives a treatment randomization number will be considered to have been randomized. 	
 • PainCart

Population	Definition / Criteria	Analyses Evaluated
UVB Safety	
 Those in the Safety Population who also perform the UVB Heat Pain detection PainCart assessments on irradiated skin. 	
 Safety (UVB Sensitivity)
UVB Intent-to-Treat (UVB-ITT)	
 Those in the ITT Population who also perform at least one UVB Heat Pain detection PainCart assessment on irradiated skin in at least one study period. 	
 PainCart UVB heat pain irradiated skin endpoint - summary
UVB Modified Intent-to-Treat (UVB-MITT)	
 Those in the MITT Population who also perform at least one UVB Heat Pain detection PainCart assessment on irradiated skin in at least two study periods. 	
 PainCart UVB heat pain irradiated skin endpoint - analysis

Refer to [Appendix 12](#): List of Data Displays which details the population used for each display.

A populations exclusion meeting will be held before unblinding of the data. The meeting minutes and list of participants excluded from the populations mentioned in Section 4: Analysis Populations will be documented and uploaded to eTMF. A summary and listing of the participants excluded from certain populations will be created.

4.1. Protocol Deviations

Important protocol deviations (including deviations related to study inclusion/exclusion criteria, conduct of the trial, participant management or participant assessment) will be summarised and listed.

Protocol deviations will be tracked by the study team throughout the conduct of the study in accordance with the Protocol Deviation Management Plan Date: 05-Sept-2019, Version 1.0.

- Data will be reviewed prior to unblinding and freezing the database to ensure all important deviations are captured and categorised on the protocol deviations dataset.
- This dataset will be the basis for the summaries and listings of protocol deviations.

A separate summary and listing of all inclusion/exclusion criteria deviations will also be provided. This summary will be based on data as recorded on the inclusion/exclusion page of the eCRF.

5. CONSIDERATIONS FOR DATA ANALYSES AND DATA HANDLING CONVENTIONS

5.1. Study Treatment & Sub-group Display Descriptors

Treatment Group Descriptions			
RandAll NG		Data Displays for Reporting	
Code	Description	Description	Order in TLF
A	3 mg/kg IV GSK3858279	GSK3858279	2
P	Placebo	Placebo	1

Treatment comparisons will be displayed as follows using the descriptors as specified:

1. GSK3858279 vs Placebo

For treatment sequence displays:

Treatment Group Descriptions			
RandAll NG		Data Displays for Reporting	
Code	Description	Description	Order in TLF
A/P/P	3 mg/kg IV GSK3858279 – Placebo – Placebo	GSK3858279-Placebo-Placebo	2
P/A/A	Placebo – 3 mg/kg IV GSK3858279 – 3 mg/kg IV GSK3858279	Placebo- GSK3858279- GSK3858279	1
		Total	3

5.2. Baseline Definitions

For all endpoints (except as noted in baseline definitions) the baseline value will be the latest pre-dose assessment with a non-missing value, including those from unscheduled visits. This study has three study periods, with each period having its own baseline which is the latest non-missing value prior to dosing in that period.

For the PainCart test, two assessments are performed at each visit except for visit Day 1 where two are performed prior to dose and two are performed after dose. The baseline value is defined as the mean of the two pre-dose assessments on Day 1 for each study period. If only one pre-dose assessment record is present on Day 1, then this value will be set as the baseline value.

For the PainCart analyses, baseline will compose of two variables:

- Subject level baseline = the mean of the three period baseline values for each subject.
- Period level baseline = Subject level baseline – Period specific baseline value.

Parameter	Study Assessments Considered as Baseline			Baseline Used in Data Display
	Screening	Day -1	Day 1 (Pre-Dose)	
Efficacy				
PainCart Assessments			X	Mean of Day 1 (Pre-Dose) Assessments
Safety				
Vital Signs			X	Day 1 (Pre-Dose)
Haematology			X	Day 1 (Pre-Dose)
Chemistry			X	Day 1 (Pre-Dose)
ECG			X	Day 1(Pre-Dose) [Mean of triplicate measurements]
Urinalysis			X	Day 1 (Pre-Dose)

Unless otherwise stated, if baseline data is missing no derivation will be performed and baseline will be set to missing.

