2.3.1. Risk Assessment

Potential Risk of Clinical Significance	Summary of Data/Rationale for Risk	Mitigation Strategy
Investigational Product (IP)		
Hypersensitivity, including injection site and infusion reactions	
The administration of any (human) mAb has the potential to induce local or systemic immunologic reactions, for example acute allergic reactions (type I) and immune complex disease (ICD) associated with the formation of anti-drug antibodies (ADA) (type III).
 
Non-Clinical
 
In a 13-week study administration of GSK3858279 by weekly IV infusion at 100 mg/kg resulted in infusion reactions after dosing on Days 22 and 29 in one female cynomolgus monkey which was successfully managed in subsequent administrations by pre-treating with anti-histamine.
 
In the 26-week study, there were inflammatory vascular changes in multiple organs of three animals (one female at 10 mg/kg/week and one male and one female at 100 mg/kg/week) as well as mesangioproliferative glomerulopathy in the kidney of the males at 10 mg/kg/week or 100 mg/kg/week, which is consistent with ICD following the formation of ADA. Nonspecific injection site reactions caused by the subcutaneous (SC) dosing route were also noted in some monkeys, which was exacerbated by the immune complex deposition in one male. These findings were considered non-adverse.
 
Animals are not predictive for ADA-mediated adverse reactions in humans, including infusion reactions, hypersensitivity reactions or
	
Participant Selection:
 
Participants with a history of sensitivity to the study medication, or a history of any drug or other allergy that, in the opinion of the investigator, contraindicates their participation, will not be permitted to enter the study.
 
Participants with renal disorders will also be excluded.
 
Participant monitoring:
 
In Part A of FiH study (207804), participants remained in the inpatient facility for 48 hours post dosing to allow adequate monitoring by trained site personnel.
 
In Part B of FiH (207804) and in this study (209973), participants will be monitored for a minimum of two hours post dosing.
 
Emergency resuscitation facilities will also be available.
 
Participants will be instructed in the Informed Consent Form (ICF) as to the signs and symptoms of hypersensitivity reactions and be

Potential Risk of Clinical Significance	Summary of Data/Rationale for Risk	Mitigation Strategy

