4.4. Justification for Dose and Washout Period

The dose level of 3mg/kg, the 2-week testing duration of each study period, the wash out period of at least 4 weeks, the IV route of administration and the post dose assessment times of Day 1, Day 2, Day 8 and Day 15 are selected for the PainCart study based on:

The dose by IV route is equivalent to the dose of 240mg SC proposed to be administered in an on-going repeat dose study in osteoarthritis patients (207804) and was administered in a healthy participant cohort in that study (3 mg/kg IV). Serum levels of total (complexed, free and partially complexed) GSK3858279 are below the lower limit of quantification (LLQ; 100 ng/mL) after 8 weeks following IV infusion at 3 mg/kg; based on data from a fully validated non-neutralising anti-idiotype capture (NNAIC) assay [GlaxoSmithKline Document Number [2020N429762_00](#)].

- Unbound CCL17 levels in serum have returned to approximately 30% of baseline at 4 weeks post dose.
 - A simulation plan was designed in order to investigate whether the statistical modelling for the PainCart assessments could control the potential properties of carry over effect. The plan details simulating carry over by varying different levels of drug accumulation in to the subsequent period, and the number of days it took for the drug to be eliminated. The results from the simulation showed even in the most extreme scenario (40% accumulation, 2 weeks reduction) the model was capable of extracting the treatment differences while controlling any potential carry over effects.
 - Given the statistical model chosen for analysis, and no increase in risk of safety, the washout period of at least 4 weeks is selected and still considered sufficient (data on file).
- Target engagement (percentage reduction from baseline of free CCL17) is above 90% within 24 hours of dosing IV and continues to 1-week post IV dose of 3 mg/kg. TE falls to 75% after 2 weeks post dose IV.
- t_{max} is at end of IV dose administration allowing PainCart testing to be scheduled at consistent fixed timepoints relative to dosing.

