2.3. Study Design

This study will be a randomized, double-blind, placebo-controlled, three-period two-treatment incomplete-block crossover study in healthy participants to investigate the effects of IV GSK3858279 on evoked pain tests in the PainCart. The study will be performed in a single centre.

In each period participants will receive either GSK3858279 or placebo in a 1:1 ratio. During the trial participants will receive both treatments, participants will receive either two doses of GSK3858279 and one dose of placebo, or two doses of placebo and one dose of GSK3858279 with equal likelihood, the order of treatment assignments will be randomised.

The total duration of the study (from signing informed consent until final follow-up visit) for each participant will be approximately 6 months. Study participation may be prolonged in the event the study is on-hold. Screening period will be a maximum of 28 days prior to study procedures, each study period will be approximately 2 weeks with at least a 4-week wash-out period between dosing (i.e. Day 1) in each of the study periods, final follow-up visit will be at approximately 8 weeks after last dose.

Participants will arrive at the research unit either one or two days before dosing, for the non-UVB-MITT and UVB-MITT group respectively. After arrival, subjects will be tested for SARS-CoV-2. Urine will be screened for the presence of drugs and an alcohol breath test will be performed. For participants with a positive urine drug screen or alcohol breath test, the treatment occasion may be rescheduled at the discretion of the principal investigator and GSK medical monitor. UVB irradiation will be applied approximately 24 hours before dosing in the UVB-MITT population only. ECG and vital signs will also be performed.

Participants will be assigned to receive treatment and pain assessments during either morning or afternoon sessions. They will continue to receive treatment and pain assessments at approximately the same time of day throughout all three study periods.

Meals will be served at the site scheduled times. Safety, PK, PD and PainCart assessments will be performed as outlined in the SoA. Baseline measurements for PainCart (2 baseline measurements) are conducted at each study period prior to dosing.

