12.4. Appendix 4: Study Phases and Treatment Emergent Adverse Events

12.4.1. Study Phases

Assessments and events will be classified according to the time of occurrence relative to the start date of the study treatment.

Study Phase	Definition
Pre-Treatment	Date/Time < Study Treatment Dose Date/Time (Period 1)
On-Treatment	Study Treatment Dose Date/Time (Period 1) ≤ Date/Time

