3.11.	Safety	LB1	Summary of Chemistry Changes from Baseline by Period	ICH E3 Present by Period	AAC [1]
3.12.	Safety	LB17	Summary of Worst-Case Chemistry Results by PCI Criteria Post-Baseline Relative to Baseline by Period	ICH E3 Present by period	AAC [1]
Laboratory: Haematology					
3.13.	Safety	LB1	Summary of Haematology Changes from Baseline by Period	ICH E3 Present by Period	AAC [1]
3.14.	Safety	LB17	Summary of Worst Case Haematology by PCI Criteria Post-Baseline Relative to Baseline by Period	ICH E3 Present by Period	AAC [1]
Laboratory: Urinalysis					
3.15.	Safety	LB1	Summary of Urine Concentration Changes from Baseline by Period	ICH E3 Present by Period	AAC [1]
3.16.	Safety	UR1	Summary of Worst-Case Urinalysis Results (Discrete or Character Values) Post-Baseline Relative to Baseline by Period	ICH E3 Present by Period	AAC [1]
ECG					
3.17.	Safety	EG1	Summary of ECG Findings by Period	IDSL	AAC [1]
3.18.	Safety	EG10	Summary of Maximum QTc Values Post-Baseline Relative to Baseline by Category by Period	IDSL	AAC [1]

CONFIDENTIAL

209973

Safety: Tables – All Safety Tables will be presented by Period unless stated otherwise.					
No.	Population	IDSL / Example Shell	Title	Programming Notes	Deliverable [Priority]
3.19.	Safety	EG2	Summary of Change from Baseline in ECG Values by Day by Period	IDSL	AAC [1]
3.20.	[Safety]	EG11	Summary of Maximum Increase in QTc Values Post-Baseline Relative to Baseline by Category by Period	IDSL	AAC [1]
Vital Signs					
3.21.	Safety	VS1	Summary of Change from Baseline in Vital Signs by Period	ICH E3	AAC [1]
3.22.	Safety	VS7	Summary of Worst-Case Vital Signs Results by PCI Criteria Post-Baseline Relative to Baseline by Period	IDSL	AAC [1]
Laboratory: Hepatobiliary (Liver)					
3.23.	Safety	LIVER1	Summary of Liver Monitoring/Stopping Event Reporting by Period	IDSL Programming Note: Subjects should be recorded under the treatment they are receiving at the time the liver monitoring/stopping event is reported, or if the liver monitoring/stopping event was reported during a washout period, under the last study treatment received. Only produce if there is a liver event	AAC [1]

CONFIDENTIAL

209973

Safety: Tables – All Safety Tables will be presented by Period unless stated otherwise.					
No.	Population	IDSL / Example Shell	Title	Programming Notes	Deliverable [Priority]
COVID-19					

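### Safety baselines reset each period can understate cumulative change after the second active dose in P/A/A and show recovery from drug as a placebo change in A/P/P; a supplementary study baseline is missing

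*SAP*

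**What the plan says.** SAP 5.2 describes "each period having its own baseline which is the latest non-missing value prior to dosing in that period". Its table applies a Day 1 pre-dose baseline to vital signs, haematology, chemistry, urinalysis and ECG (mean of the triplicate for ECG).

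The displays follow that rule. Table 3.14 is titled "Summary of Worst Case Haematology by PCI Criteria Post-Baseline Relative to Baseline by Period". Tables 3.11-3.16 and 3.18-3.22 likewise report change, worst case or maximum relative to baseline, by period. SAP 12.8.1 and 12.8.2 include limits on change from baseline: haemoglobin down 25 g/L, haematocrit down 0.075, creatinine up 44.2 µmol/L and QTc up more than 60 msec.

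SAP 5.1 lists two sequences, A/P/P and "Placebo – 3 mg/kg IV GSK3858279 – 3 mg/kg IV GSK3858279". SAP 2.3 requires "at least a 4-week wash-out period between dosing". On what remains at that point, Protocol 4.4 says "Unbound CCL17 levels in serum have returned to approximately 30% of baseline at 4 weeks post dose", and that serum drug levels "are below the lower limit of quantification (LLQ; 100 ng/mL) after 8 weeks following IV infusion at 3 mg/kg". SAP 12.4.1 defines On-Treatment as "Study Treatment Dose Date/Time (Period 1) ≤ Date/Time", with no reset between periods and no washout phase.

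**The concern.** A period baseline gives a clean within-period change only if the previous treatment's effect has gone by the next pre-dose reading. Here the shortest dosing interval is half the time after which the protocol describes drug as unquantifiable, and most of the target suppression is still present. The SAP therefore uses as baselines values that it elsewhere calls On-Treatment. The carry-over simulation cited for the 4-week interval concerns PainCart modelling; no safety parameter is mentioned.

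Three cases follow:
- **P/A/A Period 3** contains every second active dose, and its baseline may be taken about 28 days after the first. A shift that has persisted becomes the new zero; one that grows in two steps is reported as two smaller changes.
- **A/P/P Period 2** starts from a post-drug value, so recovery can appear in the placebo column.
- **A/P/P Period 3 and P/A/A Period 2** are much less exposed: the first starts at least 8 weeks after the active dose, the second after placebo only.

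P/A/A is the only sequence with repeated active dosing. Protocol 2.3.1 describes vascular and renal findings in repeat-dosed monkeys, "which is consistent with ICD following the formation of ADA", and relies partly on laboratory and urine monitoring. Creatinine or urine protein that rose after the first active dose and stayed up would read as little or no change in Period 3 of Tables 3.11, 3.12 and 3.16. The same section calls the animal findings non-adverse and not predictive for humans, so this is a reason to report repeat exposure clearly, not evidence of an expected harm.

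**Working it through.** The plan gives no figure to reproduce; the point rests on a definition.

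**Inputs**
- Minimum dose interval 28 days (SAP 2.3).
- Free CCL17 about 30% of baseline at 4 weeks (Protocol 4.4): 1 - 0.30 = 0.70 suppressed. The same section gives 75% target engagement at 2 weeks, which fits this reading.
- The exposure formula in SAP 12.6.2 adds 18*5 days. If that means five half-lives of 18 days (an assumption), the share of drug left at 28 days is 0.5^(28/18) = 0.34.
- E = effect of one active dose on a safety measure. f = share of E still present at the next pre-dose reading. The documents do not give f, so it is varied from 0 to 1. The values 0.34 and 0.70 are reference points for drug and target, not estimates for any laboratory or ECG measure.

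**Formulas for P/A/A Period 3**
- Stepwise harm: E(1+f) from the Period 1 baseline; E(1+f) - fE = E from the period baseline. Share omitted = f/(1+f).
- Persisting, non-accumulating harm: E from the Period 1 baseline; E - fE = E(1-f) from the period baseline.

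| f | Stepwise: study baseline | Stepwise: period baseline | Share omitted | Persisting: study baseline | Persisting: period baseline |
|---|---|---|---|---|---|
| 0 | 1.00E | 1.00E | 0% | 1.00E | 1.00E |
| 0.34 | 1.34E | 1.00E | 25% | 1.00E | 0.66E |
| 0.70 | 1.70E | 1.00E | 41% | 1.00E | 0.30E |
| 1 | 2.00E | 1.00E | 50% | 1.00E | 0 |

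**A/P/P Period 2.** The baseline contains fE. If that resolves during the period, the placebo change is -fE; if it persists, the change is 0.

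**Change-based limits.** For a limit L, a stepwise harm with L/(1+f) < E ≤ L exceeds L in total, but neither step exceeds it. At f = 0.70:
- QTc: 60/1.70 = 35.3, so steps of 35.3 to 60 msec.
- Creatinine: 44.2/1.70 = 26.0, so steps of 26.0 to 44.2 µmol/L.
- Haemoglobin: 25/1.70 = 14.7, so steps of 14.7 to 25 g/L.

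These windows describe the change criterion alone; the absolute limits still apply.

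**Example with the absolute limit included.** This illustrates the rule and is not an expected effect. QTc goes 390 → 430 → 470 msec, with the first step fully persisting (f = 1). The total rise is 80, above 60. Each step is 40, below 60, and 470 is below 500. Neither limit in SAP 12.8.2 is crossed in either period, although the rise from the Period 1 value exceeds the change limit.

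**The case against.** Period baselines are a usual crossover choice, and they protect against drift over a six-month study. That stands; they should stay. The other coverage is also real. Adverse event tables and the full laboratory, urinalysis, ECG and vital-sign listings do not depend on the baseline and cover at most 30 people. Investigators review every laboratory report. The vital-sign limits in SAP 12.8.3 are absolute only.

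A reader might go further and infer any of the following. The documents do not support them.

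- **That a two-step harm is never flagged, or that up to twice each limit passes unseen.** The SAP also applies absolute limits. A 50 g/L haemoglobin fall avoids the limit of 124 only from a start of at least 124 + 50 = 174 g/L. A 120 msec QTc rise avoids the limit of 500 only from a baseline of at most 500 - 120 = 380 msec. A haemoglobin path of 158 → 142 → 126 g/L escapes both haemoglobin limits, but haematocrit would fall below its 0.39 limit whenever the cell haemoglobin concentration exceeds 126/0.39 = 323 g/L (an assumed range is 320-360).
- **That the current rule detects little.** Simulation with an assumed sustained fall of 15 g/L per active dose and within-person SD of 4 to 6 g/L gives a wide gap on the change criterion alone. Once the 124 g/L limit is added (assumed means 145-155 g/L, between-person SD 9), about 66% to 95% of P/A/A participants are flagged in Period 2 or 3 under the current rule. With the Period 1 baseline, about 95% to 99% are flagged in Period 3. The simulation also assumes a Period 3 Day 27 laboratory reading that is not scheduled, and a 15 g/L step falls where one step is under 25 and two exceed it.
- **That a persisting harm disappears.** The P/A/A Period 2 baseline follows placebo, so the first-dose shift is shown there in full.
- **That no safety table uses the Period 1 baseline.** The Period 1 tables do; those for Periods 2 and 3 do not.

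**Conclusion.** The point holds as a reporting gap. In P/A/A Period 3 and A/P/P Period 2, two of the four sequence-by-period cells after Period 1, the baseline-relative summaries mix the period's own change with whatever remains from the preceding active dose. For the second active dose, the share of a stepwise harm omitted is f/(1+f): 25% at f = 0.34, 41% at f = 0.70, 50% at f = 1. A fully persisting harm reads as zero in Period 3.

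The size depends on f, which is unknown for every safety parameter, and on actual dosing intervals, since 4 weeks is a minimum. With f = 0 nothing is distorted. The table shells are not visible, so the point rests on table titles and the baseline definition. The conclusion is that these summaries can misstate cumulative change, not that harm would go undetected. It is a cheap improvement worth making.

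**What to change.** Keep the period baseline in SAP 5.2. Add a study baseline for safety: the Period 1 Day 1 pre-dose value, using the mean of the triplicate for ECG. As supplementary summaries for laboratory, urinalysis, ECG and vital signs, present by sequence and period:
- change from study baseline, alongside Tables 3.11, 3.13, 3.15, 3.19 and 3.21;
- the change-based clinical-importance, worst-case and QTc-increase categories against study baseline, alongside Tables 3.12, 3.14, 3.16, 3.18, 3.20 and 3.22.

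This needs one derived variable and no new data. The affected tables are in the later All Analysis Complete package, so the primary reporting milestone is not touched.

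The cost is more columns, plus drift from time and blood sampling in the study-baseline changes. With an assumed haemoglobin drift of 5-8 g/L per period and no drug effect, flags against the Period 1 baseline range from about 1% to 35%. The new summaries must therefore be read by comparing sequences, not one sequence alone. The change concerns reporting only and alters no dosing, stopping or withdrawal rule.
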